#### **7.4.1.2            Definition of Serious Adverse Events and SAE Reporting**

An SAE is any untoward medical occurrence at any dose that results in any of the following outcomes:

- Death
- A life-threatening event (i.e., puts the subject, in the view of the PI, at immediate risk of death)
- Inpatient hospitalization or prolongation of existing hospitalization
- A persistent or significant disability/incapacity
- A congenital anomaly/birth defect
- Important medical event that may require medical or surgical intervention to prevent one of the above outcomes

An unexpected adverse drug event is any adverse drug event the specificity or severity of which is not consistent with the current IB or, if an IB is not required or available, the general investigational plan or elsewhere in the current application.

An AE is associated with the use of the drug if a reasonable possibility exists that the event may have been caused by the drug.

SAEs that are unexpected and related to NGM621 are reportable to Regulatory Authorities. All SAEs will be reported by the PI to the Sponsor and will be reported to the responsible Ethics Committee (EC) in accordance with local requirements.

The Sponsor's assigned Safety Representative will be notified in writing (e.g., email or facsimile) within 24 hours of when an SAE is first recognized or reported. The Safety Representative will subsequently notify the Sponsor and the Sponsor's assigned Medical Monitor or designee of all reported SAEs.

#### **7.4.1.3 Classification of Severity of Adverse Event**

The severity of AEs will be categorized as shown below.

##### **Categorization of Severity of Adverse Events**

Mild	The event is minor and does not cause significant discomfort to subject or change in activities of daily living (ADL); participant is aware of symptoms, but symptoms are easily tolerated.
Moderate	The event is an inconvenience or concern to the subject and causes interference with ADL, but the participant is able to continue with ADL.
Severe	The event significantly interferes with ADL and the subject is incapacitated and/or unable to continue with ADL.
Potentially life threatening	An event/reaction in which the subject was at risk of death at the time of the event/reaction; it does not refer to an event/reaction which hypothetically might have caused death if it were more severe.

#### **7.4.1.4 Assessment of Causality of Adverse Events**

The masked, evaluating investigators should use their knowledge of the subject, the circumstances surrounding the event, and an evaluation of any potential alternative causes to determine whether an AE is considered to be related to the study drug, indicating "yes" or "no" accordingly. The following guidance should be taken into consideration (see [Table 7](#)):

- Temporal relationship of event onset to the initiation of study drug
- Course of the event, considering especially the effects of dose reduction, discontinuation of study drug, or reintroduction of study drug (as applicable)
- Known association of the event with the study drug or with similar treatments
- Known association of the event with the disease under study

- Presence of risk factors in the subject or use of concomitant medications known to increase the occurrence of the event
- Presence of non-treatment-related factors that are known to be associated with the occurrence of the event

**Table 7. Causal Attribution Guidance**

---

Is the adverse event suspected to be caused by the study drug on the basis of facts, evidence, science-based rationales, and clinical judgment?

---

YES

*There is a plausible temporal relationship between the onset of the adverse event and administration of the study drug, and the adverse event cannot be readily explained by the subject's clinical state, intercurrent illness, or concomitant therapies; and/or the adverse event follows a known pattern of response to the study drug; and/or the adverse event abates or resolves upon discontinuation of the study drug and, if applicable, reappears upon re-challenge.*

NO

*An adverse event will be considered related, unless it fulfills the criteria specified below. Evidence exists that the adverse event has an etiology other than the study drug (e.g., preexisting medical condition, underlying disease, intercurrent illness, or concomitant medication); and/or the adverse event has no plausible temporal relationship to administration of the study drug (e.g., cancer diagnosed 2 days after first dose of study drug).*

---

#### 7.4.1.5 Procedures for Recording Adverse Events

Investigators should use correct medical terminology/concepts when recording AEs on the Adverse Event eCRF. Avoid colloquialisms and abbreviations. Only one AE term should be recorded in the event field on the Adverse Event eCRF. For the purposes of reporting events of infection and inflammation, the following terms and definitions should be used:

- Iritis: the presence of inflammatory cells in the anterior chamber. Note: The presence of aqueous flare alone will not constitute iritis but should be documented as an anterior chamber flare for AE reporting purposes.
- Iridocyclitis: the presence of inflammatory cells in both the aqueous and vitreous
- Vitritis: the presence of active inflammation in the vitreous, demonstrated by the presence of inflammatory cells (trace or greater)

- Active inflammation in the vitreous should be clinically differentiated from cellular debris from prior episodes of inflammation, hemorrhage, or other causes.
- Endophthalmitis: diffuse intraocular inflammation predominantly involving the vitreous cavity but also involving the anterior chamber, implying a suspected underlying infectious cause. A culture is required prior to initiating antibiotic treatment for presumed endophthalmitis. Results of bacterial or fungal cultures, treatment given, and final ophthalmologic outcome should also be provided in the details section of the event eCRF.

Note: Trace benign, aqueous pigmented cells visible on slit-lamp examination that are caused by dilation and are not RBCs or WBCs or the result of any ocular disorder should not be recorded as an AE.

#### **7.4.1.6 Diagnosis versus Signs and Symptoms**

A diagnosis (if known) should be recorded on the Adverse Event eCRF rather than individual signs and symptoms (e.g., record only liver failure or hepatitis rather than jaundice, asterixis, and elevated transaminases). However, if a constellation of signs and/or symptoms cannot be medically characterized as a single diagnosis or syndrome at the time of reporting, each individual event should be recorded on the Adverse Event eCRF. If a diagnosis is subsequently established, all previously reported AEs based on signs and symptoms should be nullified and replaced by one AE report based on the single diagnosis, with a starting date that corresponds to the starting date of the first symptom of the eventual diagnosis.

#### **7.4.1.7 Adverse Events That Are Secondary to Other Events**

In general, AEs occurring secondary to other events (e.g., cascade events or clinical sequelae) should be identified by their primary cause, with the exception of severe or serious secondary events. However, medically significant AEs occurring secondary to an initiating event that are separated in time should be recorded as independent events on the Adverse Event eCRF. For example:

- If vomiting results in mild dehydration with no additional treatment in a healthy adult, only vomiting should be reported on the eCRF.
- If vomiting results in severe dehydration, both events should be reported separately on the eCRF.
- If a severe gastrointestinal hemorrhage leads to renal failure, both events should be reported separately on the eCRF.

- If dizziness leads to a fall and consequent fracture, all three events should be reported separately on the eCRF.
- If neutropenia is accompanied by an infection, both events should be reported separately on the eCRF.

All AEs should be recorded separately on the Adverse Event eCRF if it is unclear as to whether the events are associated.

#### **7.4.1.8        Sight Threatening Event**

For this study medically important events comprise the following sight threatening events, which are considered to be of special interest and by default are to be reported as SAEs:

- Adverse Events that caused a decrease in visual acuity of > 30 ETDRS letters or > +0.6 LogMAR lasting > 1 hour, compared with the last assessment of visual acuity at the last visit or from baseline BCVA on Study Day 1.
- Adverse Events that cause a decrease in visual acuity to the level of Light Perception or worse lasting >1 hour.
- Adverse Events that require surgical intervention (e.g., conventional surgery, vitreous tap or biopsy with intravitreal injection of anti-infectives, or laser or retinal cryopexy with gas) to prevent permanent loss of sight.
- Adverse Events associated with severe intraocular inflammation (i.e., endophthalmitis, 4+ anterior chamber cell/flare or 4+ vitritis).
- Adverse Events that, in the opinion of the Investigator, may require medical intervention to prevent permanent loss of sight.

## 8 Statistical Considerations

A detailed statistical analysis plan (SAP) will be provided and finalized prior to the study database lock or unmasking. No discrepancies are expected between the SAP and the protocol. However, if there are discrepancies between this section of the protocol and the final SAP, the SAP will override the protocol.

In general, descriptive statistics including the number of non-missing observations (n), arithmetic mean (mean), standard deviation (SD), median, minimum (min), and maximum (max) will be presented by treatment group for continuous endpoints. Frequency and percentage distribution will be presented by treatment group for categorical endpoints.

### 8.1 Analysis Sets

Subjects will be analyzed using the following analysis sets:

- Modified Intent-To-Treat (mITT) Analysis Set: All randomized and treated (with at least one dose of study drug) subjects. This analysis set will be used for all efficacy analyses and subjects will be analyzed based on the treatment group into which they are randomized.
- Per Protocol (PP) Analysis Set: a subset of subjects in the mITT Analysis Set who have no protocol deviations that affect the GA lesion assessments (by FAF). This analysis set will be used for sensitivity analyses to support the mITT analyses.
- Safety Analysis Set: All treated subjects. This analysis set will be used for all safety analyses and subjects will be analyzed based on the actual treatment they receive.
- Pharmacokinetic (PK) Analysis Set: a subset of subjects in the Safety Analysis Set who have quantifiable PK measurements post first dose. This analysis set will be used for all PK analyses and subjects will be analyzed based on the actual treatment they receive.

### 8.2 Demographics and Other Baseline Characteristics

Demographics (e.g., age, sex, race, etc.) and other baseline characteristics (body weight, iris color, etc.) will be summarized with descriptive statistics by treatment group for each analysis set.

### 8.3 Efficacy Analyses

All efficacy analyses will be performed based on data collected for study eye whenever applicable. All efficacy analyses will be performed using the mITT Analysis Set. The PP Analysis Set will be used for sensitivity analyses to support the primary and secondary efficacy analyses (the mITT analyses).

### 8.3.1 Primary Efficacy Analyses

#### 8.3.1.1 Primary Estimand

The estimand for the primary interest of this study is defined as follows:

1. Treatment: NGM621 Q4W, NGM621 Q8W, and pooled Sham (Sham injections Q4W or Q8W).
2. Population: subjects with geographic atrophy secondary to age-related macular degeneration as defined by the inclusion-exclusion criteria of the study.
3. Endpoint: rate of change in GA lesion area as measured by FAF over the 52 weeks of treatment.
4. Inter-current events and their corresponding strategies:

[figure not shown]
Intercurrent Events	Estimand Strategies
treatment or study discontinuation	Hypothetical “as own treatment group” strategy: Clinical course is the same as other subjects in the same treatment group, who had not discontinued study treatment.
treatment non-compliance	Treatment Policy strategy: All observed values of the variable are used, regardless of whether or not the subject had experienced the intercurrent event.
dose interruption	Treatment Policy strategy
initiation or adjustment of concomitant medication	Treatment Policy strategy
any other major protocol deviations	Treatment Policy strategy
intermediate events leading to intermediate missing for the FAF assessments	Hypothetical “as own treatment group” strategy

5. Population-level summary: the treatment group difference between each NGM621 group and the pooled Sham group in the mean change from baseline to Week 52 in GA lesion area as measured by FAF.

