## **6.7 Discontinuation of Subjects from Study Participation**

Subjects will be informed that they are free to withdraw from the study at any time and for any reason. The subject can also decide to discontinue study treatment but continue the remaining study assessments / visits (in this case the subject would be designated a treatment discontinuation rather than a study discontinuation). The PI may remove a subject from the study if, in the PI's opinion, it is not in the best interest of the subject to continue the study.

Subjects may be discontinued due to a change in compliance with an inclusion/exclusion criterion that is clinically relevant and affects subject safety, occurrence of AEs (Table 3), occurrence of pregnancy, or administration of non-permitted concomitant medication that might affect subject safety or study assessments/objectives. Notification of discontinuation will be made immediately to the Sponsor Medical Monitor or designee. In case of premature discontinuation of study participation, efforts will be made to perform all final EOT visit/assessments (see Table 4 and Table 5). The date the subject is withdrawn from the study and the reason for discontinuation will be recorded on the subject's eCRF. All withdrawn subjects will be followed until resolution of any AEs or until any unresolved AEs are judged by the PI to have stabilized.

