Fundus Autofluorescence (FAF) 	OU									OU							OU	
Fluorescein angiography (FA) 	OU																	
Color Fundus Photography (CFP)	OU																OU	
Microperimetry at select sites (Study eye only) 	SE	SE								SE							SE	
Serum PK 		X	X	X			X		X				X		X	X	X	
Serum ADA 		X		X			X		X				X		X	X	X	
Serum NAb 		X		X			X		X				X		X	X	X	
Serum – C3 and CH50		X	X	X					X							X	X	
CCI																		
Randomization			X															
CCI																		
Dosing (Please see Table 6)																		

OU = both eyes; SE = study eye; X = Required.

 Females of childbearing potential only; Serum pregnancy test to be conducted at screening. Urine pregnancy test to be conducted on Day 1 and Week 52 visit. If pregnancy is suspected, a serum pregnancy test may be conducted.

 For the screening visit only, it is allowable to draw blood in the order of assessments as listed in the table OR the blood draw can occur right before the FA assessment to allow for a single needle stick.

 The patient-reported outcome (PRO) measures (NEI VFQ-25 and FRI Index) will be administered by the masked site staff (except for the VA examiner) prior to any other visit assessments being performed.

 Reference [Section 7.3.12.1](#) and the pharmacy manual for details.

 A FA and SD-OCT should be performed if the development of CNV is suspected in study eye. The central reading center must confirm this finding before any intervention is initiated. See [Section 7.3.15](#) for details.

 After randomization, if a patient misses a study visit when FAF images were scheduled to be taken, the images should be taken at the next scheduled visit.

 Microperimetry is optional and applies to select sites.

 PK, Anti-drug antibody and neutralizing antibody samples will be collected at Day 1 pre-dose, Week 1 post-dose (PK collection only), Weeks 4, 16, 24, 44, 48 pre-dose, and Weeks 52 and 56.

 For subjects who discontinue early from the study, the EOT visit assessments should be performed after a minimum of 28 days has elapsed from the last administered dose. See [Section 6.7](#) for details.

 For subjects who consented to the optional sample collection.

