#### **7.3.15.1        Management of Choroidal Neovascularization (CNV)-Study Eye**

**Treatment (Study Eye):** In this protocol, only aflibercept (EYLEA®) is allowed. Follow routine clinical practice in administering aflibercept per FDA label. Treatment frequency with anti-VEGF should be based on standard of care regimens to maximize long-term visual outcomes and minimize recurrence and subject burden.

**Study Drug (Study Eye):** In subjects who developed CNV in their study eye and have a confirmed diagnosis from the Central Reading center, study drug will continue but it will be administered after anti-VEGF treatment, once the IOP has returned to a normal range (< 30 mmHg), approximately 15–30 minutes after the anti-VEGF injection. At the

physician's discretion, maneuvers such as mild ocular digital massage may be applied to the globe prior to the injection to reduce the risk of complications secondary to increased IOP.

A measurement of intraocular pressure will be obtained approximately 15 minutes after the second IVT injection by qualified unmasked site staff. If there are no safety concerns, the subject will be permitted to leave the clinic. The IOP values recorded in mmHg will be entered into the eCRF. If the IOP post dose is  $\geq 30$  mmHg, the subject should remain in clinic and be measured again approximately 30 minutes later (45–60 minutes postinjection). Pressure lowering drops are permitted at Investigator discretion. If there are no safety concerns at that time, and the IOP is  $< 30$  mmHg, the subject will be permitted to leave the clinic. The last postinjection IOP value will be recorded on the appropriate eCRF.

In the case of an acute IOP spike ( $\geq 30$  mmHg from preinjection IOP as measured at  $\geq 60$  minutes post the second injection), which causes pain and loss of vision, a paracentesis may be performed in the anterior chamber, to release some aqueous humor and relieve the pressure. The final preintervention IOP recording as well as the postintervention IOP recorded will be entered into the applicable eCRF page. If applicable, an Adverse Event eCRF page will be completed.

**Study Subject (Study Eye):** Subjects receiving CNV treatment will continue in the study until end of the study (Week 56). If subjects opt to discontinue study drug, they should still continue with study visits and assessments through Week 56.

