#### 8.3.1.2 Main Estimation

The GA lesion area (at baseline, Week 24, and Week 52) will be analyzed using a random coefficients model. The model includes terms for time (continuous variable assuming linearity) and treatment-by-time interaction. The intercept and slope of time are assumed to

be random effects with a bivariate normal distribution and an unstructured (UN) covariance matrix while the treatment-by-time interaction is assumed to be a fixed effect. CCI

Within the framework

of this model, a point estimate of the treatment group difference in the regression slope between each NGM621 group and the pooled Sham group will be provided.

[figure not shown]
The corresponding two-sided 95% confidence interval and p-value for the point estimate will also be presented.

A hierarchical testing procedure will be used to control the family-wise type-I error rate associated with the tests of the two NGM621 groups (NGM621 Q4W vs pooled Sham and NGM621 Q8W vs pooled Sham). Specifically, the comparison between NGM621 Q4W and pooled Sham will be performed first. If this test is statistically significant at the 5% level, then the comparison between NGM621 Q8W and pooled Sham will be performed. If the first test is not statistically significant at the 5% level, then the comparison between NGM621 Q8W and pooled Sham will be considered exploratory.

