### **8.3.1.3 Sensitivity Analyses**

Sensitivity analyses will be performed to assess the robustness of the main estimator of the primary estimand. These sensitivity analyses will be performed with missing data imputed by the multiple imputation approach using the Markov Chain Monte Carlo (MCMC) method, a placebo-based pattern mixture model, and a tipping point method, respectively. The details of these analyses will be provided in the SAP.

CCI

The within-subject errors are assumed to be independent and identically distributed normal random variables, and are assumed to be independent of the random intercept. The details of this analysis will be provided in the SAP.

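### The primary model has no step to set aside FAF taken after study treatment stops, so read literally it departs from the stated hypothetical strategy for subjects who stop drug but stay in follow-up

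*Combined protocol and SAP*

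**What the plan says.** **Estimand.** The intercurrent-event table in 8.3.1.1 has one row for treatment or study discontinuation, with a hypothetical strategy under which the subject follows the course of their own group: "Clinical course is the same as other subjects in the same treatment group, who had not discontinued study treatment". Non-compliance, dose interruption, changes in concomitant medication and other major deviations get treatment policy, explained as "All observed values of the variable are used, regardless of whether or not the subject had experienced the intercurrent event".

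**Estimator.** Section 8.3.1.2 states "The GA lesion area (at baseline, Week 24, and Week 52) will be analyzed using a random coefficients model". Section 8.3 adds "All efficacy analyses will be performed using the mITT Analysis Set", and 8.1 defines that set as everyone randomized and treated at least once.

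**Follow-up after stopping drug.** Section 6.7 provides that "The subject can also decide to discontinue study treatment but continue the remaining study assessments / visits". For subjects with CNV in the study eye, 7.3.15.1 says "If subjects opt to discontinue study drug, they should still continue with study visits and assessments through Week 56". For those who leave early, the footnotes to Tables 4 and 5 say "the EOT visit assessments should be performed after a minimum of 28 days has elapsed from the last administered dose", and 7.2.16 lists FAF among the procedures of that visit.

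**Sensitivity analyses.** Section 8.3.1.3 says "These sensitivity analyses will be performed with missing data imputed by the multiple imputation approach using the Markov Chain Monte Carlo (MCMC) method", and adds a placebo-based pattern mixture model and a tipping point method. Details are left to the SAP.

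**The concern.** The estimand asks how lesions would have grown had subjects stayed on their assigned treatment. The protocol keeps imaging people who have stopped, and nothing in the estimator takes those images out. An analyst who runs 8.3.1.2 as written would count growth after stopping NGM621 as growth on NGM621.

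Two things are at stake. The headline slope difference and its confidence interval would be reported against an estimand that they do not quite estimate. And with no written rule, the choice of which images enter the primary test could be made after unmasking.

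**Working it through.** **1. Does any text supply the missing step?**
- Section 8.3.1.2 names visits and a population. It gives no on- or off-treatment condition.
- Part of 8.3.1.2 is blacked out. The Main Estimation text in the Synopsis is readable at the same place and holds only the fallback covariance structure and the error assumptions. The redaction is therefore unlikely to hide such a rule.
- The imputation analyses act on missing data, and an observed off-treatment image is not missing. The nonlinear model described in the Synopsis changes only the growth curve.
- The Per Protocol set (8.1) is defined by deviations that affect the FAF assessment, not by stopping treatment.

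**2. The plan's own power figure (8.6).** Inputs: 106 per group, SD 4 mm², within-subject correlation 0.95, slopes 2, 1.4 and 1.45 mm²/yr, two-sided 5%, 10% dropout.
- SD of change = 4 × √(2 × (1 − 0.95)) = 1.265.
- Evaluable per group = 106 × 0.9 = 95.4, so SE = 1.265 × √(2/95.4) = 0.183.
- Q4W: Φ(0.60/0.183 − 1.96) = 90.6%, against about 90% stated.
- Q8W: Φ(0.55/0.183 − 1.96) = 85.1%, against 85% stated.

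The sample size reproduces; there is no error there.

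**3. Effect of leaving off-treatment images in.** The documents give neither the share who stop drug but keep FAF visits nor the growth rate afterwards. Assume that a share q of an NGM621 arm stops, that all of them stay in follow-up, and that growth returns to the sham slope. A subject who stops at fraction f of the year then keeps only f of the benefit at Week 52. With stopping times uniform over the year the mean of f is 0.5, so the estimated difference is δ × (1 − 0.5q).

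| q | Q4W (δ = 0.60) | Q8W (δ = 0.55) | Shrinkage |
|---|---|---|---|
| 5% | 0.585 | 0.536 | 2.5% |
| 10% | 0.570 | 0.5225 | 5% |
| 20% | 0.540 | 0.495 | 10% |

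- A three-visit slope calculation (Weeks 0, 24, 52) agrees: 0.585, 0.570, 0.539 for Q4W and 0.536, 0.522, 0.494 for Q8W.
- If all stop near Week 4 (f = 0.08), the slope calculation gives 0.572, 0.545, 0.489 and 0.525, 0.499, 0.449, a loss of about 5%, 9% and 18%.
- If only half of the stoppers keep their FAF visits, the losses halve. At q = 10% with uniform stopping: 10% × 0.5 × 0.5 = 2.5%.

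**4. Against the trial's precision.** The 95% CI half-width is 1.96 × 0.183 = 0.359. The Q4W shift at q = 10% is 0.60 − 0.57 = 0.03, and 0.03/0.359 = 0.08 of the half-width. At q = 20% it is 0.06/0.359 = 0.17.

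**5. Does setting those images to missing restore the target?** Simulation: 4,000 trials per scenario, 106 per arm, 10% lost at uniform times, covariance treated as known, stopping unrelated to outcome.
- Images kept: Q4W difference 0.590, 0.569 and 0.534 at q = 5%, 10% and 20%.
- Images after stopping set to missing: 0.598 to 0.602 for Q4W and 0.550 to 0.554 for Q8W, which is the hypothetical difference.
- Power at q = 10%, kept versus set to missing: 87.5% and 88.7% for Q4W, 83.7% and 82.6% for Q8W. These gaps are small and differ in direction, so the issue is what is estimated, not power.

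**The case against.** The strongest reply is that the plan is silent rather than wrong. A reader might infer that it expressly feeds off-treatment images into the primary model; no sentence says so. The table ties the use of all observed values to the treatment-policy rows, which suggests that a different data rule was meant for discontinuation. This stands as to intent, but it leaves the stated strategy without a step that carries it out.

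A reader might also infer that no planned analysis estimates the estimand. The documents do not support that. The row covers study discontinuation as well. For subjects who leave with no later FAF, a likelihood-based model under MAR already treats them like others in their group, and so does MCMC imputation. Once off-treatment FAF is set to missing, both also serve the subjects who stay.

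Third, Section 8 says that a detailed SAP will follow and will override the protocol, and the file contains no separate SAP text. If that SAP has the rule, a cross-reference is enough. But Section 8 also expects no discrepancies between the two, and 8.3.1.3 defers only details of the sensitivity analyses.

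Fourth, the effect is modest. Staying in follow-up is optional under 6.7, and 7.3.15.1 has study drug continue by default after CNV, so the group concerned may be small. Under the return-to-sham assumption the shift is toward no effect and would not manufacture a positive result. All of this stands and limits the weight of the point.

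**Conclusion.** The point holds in a limited form. For subjects who stop study treatment but stay in follow-up, the estimator in 8.3.1.2, read literally, is treatment policy, while 8.3.1.1 states a hypothetical strategy. The two should be aligned before unmasking.

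The uniform-stopping shrinkage of 2.5% to 10% is an upper illustration as regards retention, because it has every stopper keep FAF visits; earlier stopping would enlarge it. The stopping share, its timing and the off-treatment slope are all assumptions. The only related figure in the documents is the 10% dropout rate in 8.6, which is not the rate of stopping drug while keeping visits. At 10% stopping the shift is under a tenth of the confidence interval half-width. This warrants a correction to the plan; it does not threaten the trial.

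**What to change.** Add to 8.3.1.2, and to the matching Synopsis text, that for subjects who permanently discontinue study treatment, FAF acquired after discontinuation is set to missing in the main estimator and in the imputation-based sensitivity analyses. The rule should:
- fix a cut-off after the last study treatment before unmasking;
- apply alike to NGM621 and sham. A cut-off of one dosing interval plus the visit window would be 28 + 5 = 33 days for Q4W and 56 + 5 = 61 days for Q8W, so the two sham arms, pooled as one comparator, would follow different rules;
- say how early-termination FAF is handled, since it is taken at least 28 days after the last dose and may fall on either side of the cut-off.

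Add one supplementary fit of the same model on all observed FAF, labelled treatment policy, so that the effect of the rule is visible.

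The cost is one sentence, one extra model run, slightly fewer analysed images and reliance on MAR after discontinuation. If the sponsor in fact wants treatment policy for subjects who stop drug but stay, the alternative is to split the row in 8.3.1.1 and say so there.
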